2.2 Sample size calculation

The goal of the candidate algorithm is to indicate to surgeons and medical staff whether an electrode tip fold-over or electrode outside cochlea appears to have occurred, which should be confirmed radiographically. A target specificity of 98% and confidence level of 90% have been selected.

The 98% specificity target initialises the calculation of the required sample size (N). Since the specificity of the algorithms can only be estimated from a sample population, there is required to be a reasonable expectation that the specificity estimate is equal to or greater than the specificity target. To ensure that the reasonable expectation is fulfilled, the 98% specificity target is set to be the lower bound of the 90% binomial confidence interval for an estimated or measured specificity of 100%. The selected sample size must fulfil this requirement. The binomial confidence interval will be calculated using the Clopper-Pearson exact method and is denoted by Equation 1 and Equation 2:

$$P_{LB} = p : \sum_{i=0}^x \binom{n}{i} p^i (1-p)^{n-i} \approx \frac{\alpha}{2}, \quad \text{for } 0 \leq p \leq P \quad (1)$$

$$P_{UB} = p : \sum_{i=x}^n \binom{n}{i} p^i (1-p)^{n-i} \approx \frac{\alpha}{2}, \quad \text{for } P \leq p \leq 1 \quad (2)$$

where P_{LB} is the lower bound of the binomial confidence interval, P_{UB} is the upper bound of the binomial confidence interval, P is the measured probability of success, p is the probability of success, n is the number of trials, i is the number of successes, x is the measured number of successes and $\alpha = 0.1$ is the level of significance for the 90% confidence interval.

In the Clopper-Pearson method, n is the unknown input in the equation. To find n requires taking into account that there may be occurrences of electrode anomalies in the sample. The range of the possible numbers of anomalies must be estimated such that there is an expected sufficient number of samples (n) to estimate specificity. The sufficient number of samples is calculated by Equation 3 and Equation 4:

$$n = N - m \quad (3)$$

$$m = i : \sum_{i=0}^N \binom{N}{i} p^i (1-p)^{N-i} \approx 0.90, \quad \text{for } 0 \leq i \leq N \quad (4)$$

where n is the number of sufficient samples required to estimate specificity, N is the total sample size or number of patients required, i is the number of anomalies and p is the probability of an anomaly. We assume that the most prevalent anomaly condition will be a tip foldover. For p we use an estimate of 0.04139 or 4.14% which is based on the perimodiolar weighted average percentage between Grolman et al. (2009) and Zuniga et al. (2017). m is then approximately an upper bound on the number of expected tip fold-overs based on the 90th percentile of the cumulative binomial distribution. In other words, there is at least an approximate 90% chance that there will be m number of tip fold-overs or less.

Determining the sample size N is an iterative process. N is increased from 0 and for each value of N , n is calculated using Equations 3 and 4 which allows for P_{LB} to be calculated using Equation 1. Once P_{LB} is approximately 0.98 or 98%, the corresponding N is selected as the sample size.

Using the denoted method (see Appendix A) a sample size of $N = 154$ was selected which had a 89% chance of 9 or less tip fold-overs taking place, resulting in an $m = 9$ and $n = 145$. With a measured specificity (i.e. estimated specificity) of 100% and $n = 145$, the $P_{LB} = 0.9797$ which is approximately 98%.

With an algorithm target specificity of at least 98%, a target sensitivity of at least 90%, an estimated probability of a tip fold-over of 4.14%, the positive predictive value (PPV) is equal to 66.02%. This entails that after the algorithm has detected a tip fold-over, it is estimated that two thirds subset of patients will be confirmed by imaging to have a tip fold-over. The calculation of PPV is calculated by Equation 5:

$$PPV = \frac{(prevalence * sensitivity)}{(prevalence * sensitivity) + ((1 - prevalence) \times (1 - specificity))} \quad (5)$$

$$PPV = \frac{(0.0414 * 0.90)}{(0.0414 * 0.90) + ((1 - 0.0414) \times (1 - 0.98))} = 0.6602 \quad (6)$$

where in this application *prevalence* is the estimated rate of tip fold-overs.

3 Conduction of statistical analysis

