This clinical investigation will gather trans-impedance and intra-cochlear voltage measurements intra- and post-operatively. These measurements can be used to characterise the electrical properties of the electrode array and the surrounding tissue in the cochlea after insertion. This data will be used to explore the specificity of the [name] candidate algorithm. Given the low incidence of anomalous electrode position cases in normal clinical practice (Dirr et al. 2013) and the inability to deliberately generate anomalous electrode positions in patients; this study is only focussed on exploring the specificity. (negative results divided by true negative cases) of the algorithm. An exploration of the sensitivity (positive results divided by true positive cases) of the candidate algorithm is out of scope for this study. A separate in vitro study where anomalous insertions can be purposely created will be conducted to explore the sensitivity.

 For statistical purposes, it is assumed that this study will show the algorithm able to achieve  $\geq 98\%$  specificity with a 90% confidence.

For the purpose of quantifying the accuracy of a diagnostic algorithm, the following terminology is used:

- Positive case – a case in which electrode insertion results in an anomalous position.
- Negative case – a case in which electrode insertion is successful and position is not anomalous.
- True positive response – The candidate algorithm correctly detects the presence of an anomalous electrode position.
- False positive response – The candidate algorithm incorrectly indicates an anomalous electrode position when none is present.
- True negative response – The candidate algorithm correctly indicates no anomalous electrode position when none is present.
- False negative response – The candidate algorithm fails to detect an anomalous electrode position even though one is present.
- Sensitivity - the number of true positive responses divided by the number of positive cases (anomalous positions).
- Specificity - the number of true negative responses divided by the number of negative (non-anomalous) cases.
- Positive predictive value – the probability that given a positive response the electrode position is anomalous
- Negative predictive value – the probability that given a negative response the electrode position is not anomalous

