## 9 Statistical Considerations

### 9.1 Sample Size Calculation

An in-depth description of the statistical characterisation and correlation will be part of the Statistical Analysis Plan. Final statistical analysis will be conducted on a clean and complete database after database closure.

The candidate algorithm provides the ability to detect gross electrode position anomalies (eg. tip fold-over or electrode not in the cochlea). It provides binary outputs; a value of zero (negative result) or a value of one (positive result). A value of zero indicates that the algorithm concluded that an anomalous position has not occurred and the value of one indicates that the algorithm concluded that an anomalous position has occurred. To be useful as a tool that can replace routine use of X-rays and CT scans, the algorithm is required to have a minimal false positive rate. To ensure that this expectation is reasonably fulfilled, the 98% specificity target is set to be the lower bound of the 90% binomial confidence interval for the specificity of the algorithm. An iterative approach was adopted to estimate the required patient sample size which takes into account the likelihood of anomalous position events. It was assumed that the occurrence of a tip fold-over (the principal form of position anomaly under consideration) follows a binomial distribution with a positive probability of around 4% based on the weighted average percentage for tip fold-overs in pre-curved arrays reported by Grolman et al. 2009 and Zuniga et al. 2016. Using the Clopper-Pearson method a sample size of 154 was selected, which gives an 89% chance of 9 or less tip fold-overs taking place, resulting in at least 145 'normal' insertions. If the algorithm correctly diagnoses all 145 insertions, the lower bound of the two-tailed 90% confidence interval for specificity will be 97.97% which is approximately 98%. In other words, if the algorithm correctly identifies all 145 cases as 'normal' then it can be concluded that its specificity is 98% or better with 90% confidence.

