2.1 Overview

A total of 154 patients will be assessed in the statistical analysis of the data. This will serve to collect a representative sample of the variability of surgical techniques across clinics and surgeons. The confidence interval to be used in the analyses will be a 90% two-tailed. This confidence interval was deemed to be satisfactory due to the exploratory nature of the study. The statistical analyses conducted for the primary and secondary objectives will lead to the endpoints of the study.

The statistical analysis will be conducted by [REDACTED], Cochlear).

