3.1 Primary objective

The primary objective of the study is to explore the specificity of an algorithm that detects low incidence anomalies such as tip fold-overs or an electrode migration. The target maximum specificity of the algorithm has been selected to be 98%. The following steps will be run to explore the specificity up to this upper bound:

1. Run the candidate algorithms on each of the patient's data
 - Patients with 'normal' insertions (89% chance of at least 145 patients)
2. Collect the output of the algorithm

- The outputs of the algorithms will be Boolean in nature; 0 represents no tip fold-over or electrode outside the cochlea and 1 represents an tip fold-over or electrode outside the cochlea
3. Count the number of patients that have been classified as not having an anomaly by the algorithm.
 4. Conduct radiographic analysis of each insertion to classify as either normal or abnormal. Document in the latter case the reason for the classification in the anomaly category. .
 5. Calculate the percentage of patients (P) that have been correctly classified as not having an anomaly
 6. Calculate the lower bound of the 90% binomial confidence interval (P_{LB}) for the true success rate (specificity) of the algorithm using Equation 1

If the calculated lower bound of the 90% binomial confidence interval around p is equal to or greater than 98%, the candidate algorithms can be stated to have an expected specificity equivalent to or greater than 98% with 90% confidence. As explained in Section 4, the candidate will have reached the upper limit of specificity of 98% with 90% confidence if 100% of at least 145 normal insertions are correctly classified as normal.

3.2 Secondary objective 1

The first secondary objective of this study is to explore the association or relationships between the trans-impedance, intra-cochlear voltage measurements and NRT thresholds and the intra-cochlear electrode position. This will be conducted by:

1. Measuring the intra-cochlear electrode array position for 22 electrodes for each patient from CT images
2. Univariate and multivariate analysis
 - a. Visualisation (descriptive statistics)
 - b. Feature extraction
 - c. Correlation and ANOVA analysis
 - d. Statistical modelling

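### The sample size is said to ensure a reasonable expectation of meeting the 98% specificity target, but it assumes a perfect observed result and gives no probability of success

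*SAP*

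**What the plan says.** SAP 2.2 sets the aim of the sizing: "there is required to be a reasonable expectation that the specificity estimate is equal to or greater than the specificity target". The means is to make 98% the lower limit of the 90% binomial interval "for an estimated or measured specificity of 100" percent. Protocol 9.1 gives the same reasoning: "To ensure that this expectation is reasonably fulfilled, the 98% specificity target is set to be the lower bound". Protocol 3, footnote 2, adds that for statistical purposes "it is assumed that this study will show the algorithm able to achieve" at least 98% specificity with 90% confidence.

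The interval is Clopper-Pearson. SAP 2.1 states: "The confidence interval to be used in the analyses will be a 90% two-tailed". With alpha = 0.1, this leaves 5% in the lower tail.

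SAP 3.1 then states success in two ways. The first is a lower limit equal to or above 98%. The second is correct classification of every one of at least 145 normal insertions. Both documents state H0 (specificity below 98%) and H1 (98% or more).

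The one probability given is 89%, the chance of 9 or fewer tip fold-overs among 154 implantations. Neither document states an assumed true specificity or the probability that the rule will be met.

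**The concern.** A claim that a sample size gives a reasonable expectation of success is a claim about probability. It needs an assumed true specificity and the chance of passing at that value. Here the observed result is set at its maximum instead, which only shows that the target can be reached if nothing goes wrong.

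This matters because the plan has formal hypotheses and a pass rule, and because Protocol 9.1 ties high specificity to replacing routine imaging. A reader of the plan cannot tell that an algorithm whose true specificity is above 98% may well not pass. SAP 3.1 defines the positive conclusion only, so the meaning of a result with one or two false positives is left open.

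**Working it through.** **Inputs from the documents.** N = 154. Fold-over rate 9/(0.48 × 303 + 72) = 9/217.44 = 0.04139 (SAP 2.2 and Appendix A). Anomaly allowance m = 9, so n = 145. Two-sided 90% Clopper-Pearson interval. Target 98%.

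**Assumed input.** The true specificity s is not in the documents; it is varied from 98% to 99.9%.

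**1. The plan's own figures.** P(X ≤ 9 | 154, 0.04139) = 0.8925, the stated 89%. With no false positives the lower limit is 0.05^(1/n). For n = 145 this is 0.05^(1/145) = 0.97955. The stated 0.9797 comes from the Appendix A grid search, which accepts a tail area within ±0.002 of 0.05 and so returns 0.97975. N = 154 and n = 145 reproduce.

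**2. Effect of one false positive.** The lower limit is the 5% quantile of a Beta(x, n − x + 1) distribution.

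- 144/145: 96.77% (upper limit 99.96%)
- 153/154, with no anomalies at all: 96.96%
- 234/235: 97.997%; 235/236: 98.006%

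One error is therefore tolerated only from 236 normal insertions, and the study can have at most 154.

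**3. The two criteria in SAP 3.1 differ.** 145/145 gives 97.96%, which is below 98%. The limit is 97.996% at 148/148 and 98.01% at 149/149, so the literal rule needs 149 normal insertions, that is, at most 5 anomalies. P(X ≤ 5 | 154, 0.04139) = 38%.

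**4. Probability of success.**

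- A: no false positive in exactly 145, s^145.
- B: at least 145 normal insertions and no false positive, Σ(k = 0 to 9) Bin(k; 154, 0.04139) × s^(154 − k).
- C: literal lower limit ≥ 98%, the same sum for k = 0 to 5.

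| True specificity (assumed) | A | B | C |
|---|---|---|---|
| 98% | 5% | 4% | 2% |
| 98.5% | 11% | 10% | 4% |
| 99% | 23% | 20% | 8% |
| 99.5% | 48% | 42% | 18% |
| 99.9% | 86% | 77% | 33% |

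Under A, an 80% chance needs s = 0.8^(1/145) = 99.85%.

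**5. What a miss would mean.** The interval for 144/145, 96.8% to 99.96%, contains 98% and most of the range above it. With 145 normal insertions the upper limit first falls below 98% at 7 false positives (138/145: 97.7%; at 139/145 it is still 98.2%).

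**The case against.** The strongest reply is that nothing is hidden. Both documents say repeatedly that the bound applies if every normal insertion is classified correctly. SAP 3.1 also calls 98% a maximum and an upper limit, so it can be read as the most that this sample could show. The study is described as exploratory and descriptive. All of this stands, and it makes the point one of missing operating characteristics, not of wrong arithmetic. It does not support the word ensure, because disclosing a condition does not make the condition likely. In SAP 2.1 the exploratory nature justifies the 90% level only, and a pass rule remains.

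A second reply is that the quoted sentence speaks of the estimate reaching the target. Read as a point estimate, up to 2 false positives in 145 would pass (143/145 = 98.6%; 142/145 = 97.9%), with an 82% chance at a true 99%. But the next sentence of SAP 2.2 moves to the lower limit, and SAP 3.1 decides on the lower limit.

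Some stronger readings are tempting but not supported:

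- A reader might infer that the 89% is offered as a probability of success. The documents always attach it to the number of fold-overs or of normal insertions, so it needs no disclaimer.
- A reader might infer that a miss will be reported as specificity below 98%. No passage says so, and SAP 3.1 already requires the percentage and the lower limit.
- A reader might want to recover precision by analysing a continuous decision value against the algorithm's threshold. Protocol 3 mentions a threshold parameter, but SAP 3.1 says "The outputs of the algorithms will be Boolean in nature", and neither document says that an underlying score can be exported.

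**Conclusion.** The concern holds as a fault in the planning statement. The property claimed in SAP 2.2 and Protocol 9.1 is not shown. Success requires zero false positives, and its probability is never given. If the criterion is 100% of at least 145, the chance runs from 4% to 77% over true specificities of 98% to 99.9%. If it is a lower limit of at least 98%, it runs from about 2% to 33%.

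These figures assume independent insertions with a common specificity, the SAP's fold-over rate, and no loss of normal cases for any other reason. Further losses, such as the other insertion events excluded under Protocol 9.3, would lower the chance of having enough normal insertions.

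That a good algorithm will probably miss the target does not follow from the documents alone. It depends on the assumed true specificity: at 99.9%, 145/145 is the likely result (86%). Nor does the finding show that 154 is miscalculated under the method the SAP describes.

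**What to change.** Leave N at 154 and change the text of SAP 2.2 and 3.1 and Protocol 9.1, with footnote 2 of Protocol 3 brought into line.

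1. Reconcile the two criteria in SAP 3.1 first. Either keep 100% of at least 145 and state the demonstrable bound as 97.9% (97.96% rounded down), or keep the 98% limit and state that 149 normal insertions are needed.
2. Replace the sentences that claim to ensure the expectation. Say that the sample gives a lower bound of about 98% only if there are no false positives, and give the success probabilities for the chosen criterion (column B or C above) over a range of true specificities.
3. State that one or more false positives means that 98% has not been shown, reported as the estimate with its 90% interval. Add that failing the rule is not in itself evidence of specificity below 98%; that would need the upper limit to lie below 98%.

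The cost is a wording amendment and a less favourable planning statement. No extra subjects or data are needed.

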3.1 Primary objective

The primary objective of the study is to explore the specificity of an algorithm that detects low incidence anomalies such as tip fold-overs or an electrode migration. The target maximum specificity of the algorithm has been selected to be 98%. The following steps will be run to explore the specificity up to this upper bound:

1. Run the candidate algorithms on each of the patient's data
 - Patients with 'normal' insertions (89% chance of at least 145 patients)
2. Collect the output of the algorithm

- The outputs of the algorithms will be Boolean in nature; 0 represents no tip fold-over or electrode outside the cochlea and 1 represents an tip fold-over or electrode outside the cochlea
3. Count the number of patients that have been classified as not having an anomaly by the algorithm.
 4. Conduct radiographic analysis of each insertion to classify as either normal or abnormal. Document in the latter case the reason for the classification in the anomaly category. .
 5. Calculate the percentage of patients (P) that have been correctly classified as not having an anomaly
 6. Calculate the lower bound of the 90% binomial confidence interval (P_{LB}) for the true success rate (specificity) of the algorithm using Equation 1

If the calculated lower bound of the 90% binomial confidence interval around p is equal to or greater than 98%, the candidate algorithms can be stated to have an expected specificity equivalent to or greater than 98% with 90% confidence. As explained in Section 4, the candidate will have reached the upper limit of specificity of 98% with 90% confidence if 100% of at least 145 normal insertions are correctly classified as normal.

3.2 Secondary objective 1

The first secondary objective of this study is to explore the association or relationships between the trans-impedance, intra-cochlear voltage measurements and NRT thresholds and the intra-cochlear electrode position. This will be conducted by:

1. Measuring the intra-cochlear electrode array position for 22 electrodes for each patient from CT images
2. Univariate and multivariate analysis
 - a. Visualisation (descriptive statistics)
 - b. Feature extraction
 - c. Correlation and ANOVA analysis
 - d. Statistical modelling

Univariate analysis will first involve visualising the data and comparing the visualisation between electrode positing. The visualisation can be conducted by using simple scatterplots with the independent variables, or subcomponents of the independent variables, on the x-axis and the dependent variable on the y-axis. With multidimensional measurements, plots such as mesh grids or surface plots will yield more value. This will aid the statistician to visually identify any patterns, trends or key features between the variables and note them for further investigation.

More “*complex*” data or measurements can be processed, transformed or reduced to a more meaningful single value or a set of values that represents the original data and may have explanatory power. This process is feature extraction. Feature extraction can be governed by the visualisation stage or engaging in a set of routines as calculating the determinant or Eigen values of multidimensional data, means, medians, variances, converting continuous

variables into interval variables etc. Key values extraction may also include filtering or smoothing the data.

Electrode position and associated values of independent variable (e.g. measurements and/or key features) and be composed into arrays. This allows for the Pearson's correlation statistics to be calculated. The correlation statistic indicates whether or not linear relationship between two variables and the sign of the relationship. The statistic ranges from -1 to 1. A value of -1 entails that the two variables are negatively linearly related. A value of 1 entails that the two variables are positively linearly related. A value of 0 entails that there is no linear relationship. The resultant statistics will be tested for statistical significance. If the relationship is not statistically significant with a 90% confidence interval or has a low correlation, it is very unlikely it will be a candidate to be a primary explanatory variable. The correlation statistic may be indicative of a higher order relationship.

Interval, nominal or ordinal variables will be analysed using parametric or non-parametric methods depending on the observed distribution of the experimental data. Electrode positioning data will be grouped according to their associated value of the interval, nominal or ordinal variables. The values of the nominal or ordinal variables will be considered as treatments. The treatment effect will be analysed for magnitude and statistical significance. Distributions will be tested for normality using the Shapiro-Wilk test. Parametric ANOVA may include the use of Welch's t-test. Non-parametric tests may include Mann-Whitney U test or the Kruskal-Wallis test.

The previous steps will have identified key variables to be included in statistical models that describe relationships between measurements and electrode positioning. These key variables may be related to one another. Visualisation and correlation analysis will aid to identify variables that are related to one another. Variables that are identified to have possible relationships will be controlled for when statistically modelling.

Statistical modelling will involve determining a relationship the independent variables that result in a best fit or least error. The visualisation phase, key feature extraction and correlation analysis will define the variables that should be included in the model and what is the relationship between the variables. Candidate models will include regression, logistics regression or machine learning techniques such as feed-forward back-propagation neural networks. Models will be developed in a stepwise approach. Variable inclusion will proceed with the variables identified to be the most significant to the least significant. For regression analysis, for each step statistical tests will be performed such as f-test and t-tests on regression coefficients. If the output of the test does not indicate that the coefficients are statistically significant, the variables will be discounted. Accuracy statistics such as R^2 , correlation and root mean square error will be calculated. If the accuracy does not increase, the variables will be discounted.

The end results will be statistical models that explain the relationship between intra-cochlear electrode positions and trans-impedance, intra-cochlear voltage and NRT thresholds. This information will substantially influence the development of candidate algorithms.

3.3 Secondary objective 2

The second secondary object of this study is to investigate the changes in the trans-impedance, intra-cochlear voltage and the NRT thresholds over time to identify the stability of the measurements. The contact points for the patients in the study are surgery, activation (4

weeks after surgery) and 3 months post-operative. Investigating how the measurements change throughout time will involve:

- Excluding patients that have been confirmed (by imaging) to have an anomalous position.
- Characterising the measurements at each contact point
- Characterising the changes in measurements between the contact points

Characterising the measurements at each contact point involves:

- Visualising the distributions (e.g. scatter plots, frequency histograms, boxplots, etc.)
- Calculating the distribution statistics (e.g. normality, mean, median, standard deviation, confidence intervals around mean and medians)
- Parametric or non-parametric ANOVA between the distributions of each contact point

Characterising the changes in measurements between the contact points involves:

- For each patient calculating the difference between the measurements at each time point to create difference distributions
- Visualising the difference distributions (e.g. scatter plots, frequency histograms, boxplots, etc.)
- Calculating the distribution statistics (e.g. normality, mean, median, standard deviation, confidence intervals around mean and medians)

A parametric or non-parametric (Friedman) ANOVA will be conducted on the difference distributions of the periods between each contact point to establish the significance of the time factor.

This information will provide guidance on the time from surgery during which the findings of candidate algorithms can be considered valid.

3.4 Secondary objective 3

To ensure the correct handling and storage of patient data for the study, study measurements and metadata will be uploaded to a clinical study database. The database will be structure accordingly:

- A section storing patient information such as:
 - Identifier
 - Implant
 - Demographics
 - Medical history
 - Adverse events
 - Medical professionals' notes and comments
 - Surgical variables
 - Nature of insertion

- A section storing CT images, the operating medical professionals notes and electrode positioning
- A section storing trans-impedance measurements, the measurement parameters and the point in time the measurement was taken
- A section storing intra-cochlear voltage measurements, the measurement parameters and the point in time the measurement was taken
- A section storing NRT measurements, the measurement parameters and the point in time the measurement was taken
- A section storing Cochlear Implant Fitting Software CDX files

An independent researcher (i.e. not the person who developed the database) will determine whether the information has been correctly uploaded to the database, the integrity of the data in the database and whether patient information has been sufficiently de-identified.

4 Quality control of statistical analysis

The statistical analysis plan will be undertaken primarily using the Python programming language with the Numpy and Scipy libraries. Other programming languages or software packages such as Matlab, SAS or Excel may also be used. The analysis plan will be:

1. Statistical analysis will take place once all of the data has been collected
2. Programmed to retrieve the objective outputs
3. The code and the outputs will be reviewed to determine whether or not what was stipulated in the objectives have been met and whether or not the outputs are in line with what domain experts' expectations

Code review and output review will be carried out by an independent person (i.e. not identical to the primary programmer).

If a patient has missing or spurious data, the data that is remaining of quality will be used in the clinical investigation. Patients that drop-out will cause only the data that has been collected to be analysed.

5 Derived data

All derived data as described in the conduction of the statistical analysis will be described in full detail with the steps taken to calculate or produce the derived data.

6 Analysis populations

All patients will be included in the analysis unless a patient has been confirmed to have an anomalous position.

7 Bibliography

Publication Of The American Otological Society, American Neurotology Society [And] European Academy Of Otology And Neurotology, vol. 38, no. 2, pp. 199-206.
Available from: 10.1097/MAO.0000000000001283. [15 March 2017]

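### SAP 3.1's success rule (lower limit at least 98%) needs 149 error-free normal insertions, but its next sentence and Protocol 9.1 accept 145, and Equation 1 as printed cannot give the limit

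*SAP*

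**What the plan says.** SAP 2.1 specifies a two-tailed 90% interval for the analyses. SAP 2.2 names the method: "The binomial confidence interval will be calculated using the Clopper-Pearson exact method and is denoted by Equation 1 and Equation 2". It sets 98% as the lower limit to be reached when the measured specificity is 100%, and adds: "The selected sample size must fulfil this requirement". The search for N is looser. It stops once the lower limit "is approximately 0.98 or 98%, the corresponding N is selected as the sample size". The result is N = 154, with an allowance of m = 9 anomalies and n = 145 normal insertions, and a stated limit of 0.9797.

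SAP 3.1 gives the decision rule. Step 6 calculates the lower limit "for the true success rate (specificity) of the algorithm using Equation 1". Success is then defined as: "If the calculated lower bound of the 90% binomial confidence interval around p is equal to or greater than 98" per cent. The following sentence refers to Section 4 for the explanation and states that "the candidate will have reached the upper limit of specificity of 98% with 90% confidence if 100% of at least 145 normal insertions" are classified correctly.

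Protocol 9.1 agrees with the second sentence. It says: "If the algorithm correctly diagnoses all 145 insertions, the lower bound of the two-tailed 90% confidence interval for specificity will be 97.97" per cent, calls this approximately 98%, and goes on to say that if the algorithm identifies "all 145 cases as 'normal' then it can be concluded that its specificity is 98% or better with 90% confidence". The hypotheses (Protocol 7, SAP 1.4) put H1 at a specificity of 98% or more.

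**The concern.** The two sentences of the rule in SAP 3.1 are not equivalent. The first is a strict inequality with no rounding. The second, and the Protocol 9.1 conclusion, accept a count whose limit is below 98% even on the documents' own figure of 97.97%. If the study ends with 145 to 148 normal insertions and no false positive, one sentence passes the algorithm and the other fails it. The count of 145 is the design point, so this is not a remote corner of the plan.

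The formula that step 6 prescribes does not resolve the matter, because as printed it cannot return a lower limit in the planned success case. The Appendix A code does not resolve it either, because its tolerance makes it disagree with the exact method at 148.

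What is at stake is how the primary result is described against the 98% target. The study is exploratory, and surgeons receive no feedback from the algorithm, so patient care is not affected.

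**Working it through.** **Inputs.** Two-tailed 90% interval, so 0.05 in the lower tail (SAP 2.1, 2.2). Clopper-Pearson exact (SAP 2.2). N = 154 (SAP 2.2). Fold-over rate from Appendix A: (5 + 4) / (0.48 × 303 + 72) = 9 / 217.44 = 0.04139.

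**The plan's own figures.** P(9 or fewer fold-overs among 154) = 0.8925, the stated 89%. The Appendix A search (8000 grid points, tail accepted within 0.05 ± 0.0020, last match kept) gives 0.97975 at 145/145, which is the printed 0.9797. Both reproduce.

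**Exact limit.** With all n cases correct, the lower limit solves p^n = 0.05, so it is 0.05^(1/n).

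| Normal insertions, all correct | Exact lower limit | Tail at 98%, 0.98^n |
|---|---|---|
| 145 | 97.955% | 0.0534 |
| 146 | 97.969% | 0.0524 |
| 147 | 97.983% | 0.0513 |
| 148 | 97.996% | 0.0503 |
| 149 | 98.010% | 0.0493 |

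The threshold is ln(0.05) / ln(0.98) = 148.28, so 149 is the first count that passes. The shortfall at 145 is 98 − 97.955 = 0.045 percentage points. The Appendix A search overstates the limit slightly because it keeps the largest grid value inside its tolerance; at 148 it returns 98.012%, a pass, where the exact limit fails.

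**How often the sentences conflict.** With X excluded insertions and true specificity s, a conflict needs X from 6 to 9 (148 to 145 normals) and no false positive: the sum over k = 6 to 9 of P(X = k) × s^(154 − k), with X binomial(154, exclusion rate). The documents give 98% only as a target, so s is assumed. The 8% rate is also an assumption, used to show the effect of the wider exclusions in Protocol 9.3.

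| Assumed true specificity | Rate 4.139% (fold-overs only) | Assumed rate 8% |
|---|---|---|
| 98% | 2.6% | 1.0% |
| 99% | 12% | 4.4% |
| 99.5% | 24% | 9.2% |
| 100% | 51% | 19% |

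**Chance of reaching 149.** This requires at most 154 − 149 = 5 exclusions. At 4.139%, P(X ≤ 5) = 38%, against 89% for at least 145. Both assume that only fold-overs are excluded and no data are lost.

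**Equation 1.** As printed it sums the binomial terms from i = 0 to x and sets the sum to α/2. At x = n the sum is 1 for every p, so it never equals 0.05. At x = 144, n = 145 its root is 0.99965, which is the upper limit and lies outside the stated range p ≤ P = 144/145 = 0.9931. The true lower limit there, 0.9677, is the root of the sum printed in Equation 2. The Appendix A code sums from x to n for the lower bound, which is correct. The sums in the two printed equations are interchanged.

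**The case against.** The strongest reply is that nothing is hidden. Protocol 9.1 and SAP 2.2 print a limit below 98% and call it approximately 98%, and Protocol 9.1 and SAP 3.1 both name 145/145 as sufficient, so the intended verdict can be read before any data. The evidence at 145/145 is also not weak: 1 − 0.98^145 = 94.7% one-sided confidence that specificity is at least 98%, and a one-sided 90% limit would be 0.10^(1/145) = 98.42%. The shortfall exists only against the lower end of the two-tailed interval. Equation 1 fails visibly rather than giving a wrong number, the method is named correctly, the code has the right sum, and SAP 4 requires independent code review.

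Most of this stands, and it limits what may be inferred. A reader might conclude that the claim of 98% with 90% confidence at 145/145 is false. It is not, as a one-sided statement. A reader might also conclude that the verdict on H1 would be left entirely open until the results are seen. The documents signal their intention too clearly for that.

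What does not stand is that the disclosure removes the contradiction. The approximate wording belongs to the sample-size text. The rule in SAP 3.1 has no tolerance, and SAP 2.2 says that the sample size must meet the requirement.

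**Conclusion.** The point holds as an inconsistency in the decision rule and an error in a printed formula; it should be fixed. Under the two-tailed 90% Clopper-Pearson interval that the plan specifies, 145/145 misses the written 98% threshold by 0.045 percentage points, and 149 error-free normals are needed. The conflict figures rest on N = 154, independent insertions, no lost data and an assumed true specificity. They fall if the wider exclusions in Protocol 9.3 push the exclusion rate well above 4.139%, because fewer than 145 normals fails both sentences. The 51% figure is for an algorithm that never errs and should not be read as the expected chance.

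The documents do not support reading this as a need for more patients: the contradiction can be removed by wording alone.

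**What to change.** Before the algorithm is run, and keeping the 98% rule and the hypotheses as they are:

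- Replace 145 by 149 in the last sentence of SAP 3.1 and in the Protocol 9.1 statement that concludes 98% or better with 90% confidence.
- In SAP 2.2 and Protocol 9.1, correct the printed limit at 145/145 to 0.9796 (97.96%), and state that m = 9, n = 145 does not reach 98%.
- State that reaching 149 allows at most 5 excluded insertions. Amend Protocol 8.1 footnote 4 accordingly, and describe the 9 in Protocol 8.1 and 8.3.7 as the sizing allowance only.
- Beside the 89% for 145, give the 38% chance of at least 149 normal insertions, noting that it assumes only fold-overs are excluded.
- Compute the limit exactly, as beta.ppf(0.05, x, n − x + 1), in place of the Appendix A tolerance search.
- Correct Equation 1 to sum from i = x to n and Equation 2 to sum from i = 0 to x.
- In SAP 3.1, change the reference to Section 4 (quality control) to Section 2.2.

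The cost is wording in two documents, two pairs of summation limits and one line of code, with no new patients or data. The downside is that a less favourable planning figure, 38%, is stated openly. The change does not make the rule more tolerant of errors: one false positive among 154 normals gives a limit of 96.957% and still fails.
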